11.1.6 Safety analysis variables

The safety analysis variables during the clinical observation period include:

- Frequency and extent of adverse events (AEs), serious AEs (SAEs), and treatment-emergent adverse events (TEAEs). TEAEs are defined as all AEs with onset or worsening after treatment with randomized IMP within 4 weeks after each PDT cycle (until Visit 4 or Visit 7, respectively).
- New AK, NMSC and melanoma, including location of lesion(s).
- Local skin reactions at the treatment field(s) assessed by the investigators.
- Local discomfort or pain during illumination, reported by the subjects.
- Vital signs.
- Safety laboratory.
- Physical examinations.

The safety analysis variable during the FU period include:

- Any local (S)AEs or conditions within the treatment field(s) that may be relevant for proper assessment of the recurrence of the treated lesions. Any relevant SAE or serious adverse reaction (SARs).
- New NMSC and melanoma, including location of lesion(s).
- New AK lesions within the treatment field(s) and treated subarea(s).

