## Table 1: Visit terminology

Notation in protocol	Notation used for TLG presentation
Visit 1, Screening (≤ 4 weeks prior to PDT-1)	Screening
Randomization at Visit 2, PDT-1 (Baseline)	Randomization
Visit 2, PDT-1 (Baseline)	PDT-1
Not applicable	Baseline 
Visit 3, PDT-2 (1-2 weeks post-PDT-1)	PDT-2
Phone call 1 (1 week ± 2 days post-PDT-2)	1 week post-PDT-2
Visit 4 (5 weeks ± 1 week post-PDT-1)	5 weeks post-PDT-1
Visit 5, PDT-3 (12 weeks ± 1 week post-PDT-1)	PDT-3 / 12 weeks post-PDT-1
Visit 6, PDT-4 (1-2 weeks post-PDT-3)	PDT-4
Phone call 2 (1-week ± 2 days post-PDT-4)	1 week post-PDT-4
Visit 7 (5 weeks ± 1 week post-PDT-3)	5 weeks post-PDT-3
Visit 8 (12 weeks ± 1 week post-PDT-3)	12 weeks post-PDT-3
Not applicable	12 weeks after start of the last PDT cycle 

 Baseline is defined as last non-missing value until PDT-1, i.e. non-missing observation on PDT-1 visit or non-missing observation on Screening visit will be used as Baseline value. Non-missing observation on PDT-1 visit will be used as Baseline value if assessment was performed before treatment (before drug application and light treatment). Non-missing observation on Screening visit will be used as Baseline value in following cases:

- if no assessment on PDT-1 visit was performed and non-missing observation on Screening visit is available,
- if assessment on PDT-1 visit was performed after treatment (after drug application and light treatment) and non-missing observation on Screening visit is available,
- if assessment on PDT-1 visit was performed before treatment (before drug application and light treatment) and assessment observation is missing and non-missing observation on Screening visit is available.

If the absolute change from Baseline is calculated for a parameter or Baseline characteristics are presented, this artificial visit will be displayed in the corresponding tables and Baseline value will be indicated in corresponding listings.

 For complete responders, Visit 5 will be used as 12 weeks after the start of the last PDT cycle visit, for non-responders or partial responders, Visit 8 will be used. For analysis reasons, these visits will be combined to the artificial visit "12 weeks after start of the last PDT cycle" and will be displayed in the corresponding tables and used value will be indicated in corresponding listings.

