#### Frequency and extent of TEAEs, including SAEs

TEAEs are defined as all AEs with time of onset on or after the time of treatment with randomized IMP within 4 weeks (28 days) after each PDT cycle. If time of onset of AEs is not within 4 weeks (28 days) after each PDT cycle, but is identified to be at least possibly related to IMP or medical device, AEs will be assumed as TEAEs. The reference dates will be calculated as date of last PDT within each PDT cycle + 28, i.e. date of PDT-2 and/or PDT-4, respectively. If PDT-2 and/or PDT-4 are not available, the dates of PDT-1 and/or PDT-3 will be used for calculation of reference dates. These reference dates will be used for assignment of TEAEs. If unclear due to incomplete start time/date of AE or PDT, AEs will be assumed as TEAEs, as far as end time/date of AE is not before first treatment in first PDT cycle. AEs and TEAEs will be summarized and tabulated according to primary system organ class and preferred term displaying the number of events as well as counts and percentages on a subject basis per treatment arm.

[figure not shown]
Additionally, TEAEs by sex, TEAEs by age group I, serious TEAEs and TEAEs by intensity (mild/moderate/severe/unknown) will be tabulated. Related TEAEs (defined as possibly, probably, or definitely related, or with missing relationship) will be presented by intensity overall (related to IMP or related to medical device), related to IMP only, related to IMP and medical device and related to medical device only. Additionally, TEAEs by relationship (unrelated / unlikely related / probably related / probably related / definitely related) will be presented related to IMP and related to medical device separately.

TEAEs leading to death and TEAEs resulting in discontinuation of study will be tabulated if more than 5 events are observed. Specification of any action taken documented on AE page as 'Withdrawal from study' will be used for detection of TEAEs resulting in discontinuation of study.

A listing of subjects with TEAEs will be provided for all TEAEs reported. Non-TEAEs, i.e. AEs with onset before treatment or later than 4 weeks after each PDT cycle, will be listed separately for all subjects enrolled. In listings, the start day of the AE relative to start of treatment will be calculated for complete start dates only. Duration of events is only calculated for complete start and end dates.

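### SAP 4.5 describes no by-arm table of all SAEs and all deaths; late serious events judged unrelated or unlikely related fall outside the serious-event table

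*SAP*

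**What the plan says.** Protocol 11.1.6 opens its list of safety variables for the clinical observation period with "Frequency and extent of adverse events (AEs), serious AEs (SAEs), and treatment-emergent adverse events (TEAEs"; SAP 2.4 repeats the item. Protocol 8.2 has AEs collected from informed consent to Visit 5, or to Visit 8 for retreated subjects.

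SAP 4.5, under the heading on TEAEs and SAEs, sets out the tables:

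- All AEs and all TEAEs are tabulated per arm by system organ class and preferred term, with events, subject counts and percentages.
- For serious events: "Additionally, TEAEs by sex, TEAEs by age group I, serious TEAEs and TEAEs by intensity (mild/moderate/severe/unknown) will be tabulated".
- For fatal events and withdrawals: "TEAEs leading to death and TEAEs resulting in discontinuation of study will be tabulated if more than 5 events are observed".
- For the rest: "Non-TEAEs, i.e. AEs with onset before treatment or later than 4 weeks after each PDT cycle, will be listed separately". SAP 4.9 sorts listings by treatment group.

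The end of the TEAE window is fixed by "The reference dates will be calculated as date of last PDT within each PDT cycle + 28". A later event that "is identified to be at least possibly related to IMP or medical device, AEs will be assumed as TEAEs", and unclear dates also default to TEAE. The SAP's section on changes from protocol explains the adapted TEAE definition but says nothing about SAEs outside it.

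**The concern.** SAEs are named as a variable in their own right for the whole observation period, but the summary described covers only the part that meets the TEAE definition. For a serious event with late onset, entry into the by-arm count depends on the investigator's causality judgement: possibly related or stronger is in, unrelated or unlikely related is out. A comparison of serious events between arms should not depend on that judgement, particularly as Protocol 1.2 expects visible application-site effects in the active arm.

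At stake is whether a table gives the number of subjects with any SAE, and the number of deaths, per arm with a denominator. With 149 active and 37 vehicle subjects planned, counts will be small and unequal in base, so explicit denominators matter.

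**Working it through.** The documents give no figure for the share of a cycle outside the TEAE window, so there is none to reproduce.

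**Inputs**
- Window end: last PDT of the cycle plus 28 days (SAP 4.5).
- Gap *g* between the two PDTs of a cycle: 7 to 14 days (SAP Table 1, "Visit 3, PDT-2 (1-2 weeks post-PDT-1"); *g* = 0 if the second PDT was not given, since the SAP then uses the first PDT date.
- Length *L* from the first PDT to the 12-week visit: 84 days, range 77 to 91 (SAP Table 1, "Visit 5, PDT-3 (12 weeks ± 1 week post-PDT-1"). Cycle 2 has the same timing from PDT-3.

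**Share outside the window** = (*L* − (*g* + 28)) / *L*

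| *L* | *g* | Days inside | Days outside | Share outside |
|---|---|---|---|---|
| 84 | 7 | 35 | 49 | 58.3% |
| 84 | 14 | 42 | 42 | 50.0% |
| 77 | 14 | 42 | 35 | 45.5% |
| 91 | 7 | 35 | 56 | 61.5% |
| 84 | 0 | 28 | 56 | 66.7% |

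The share is 50.0-58.3% on the nominal schedule and 45.5-61.5% with the ±1 week visit window, provided both PDTs are given.

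**Where a serious event in a treated subject goes, by onset and causality**

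| Onset | Causality | Serious-TEAE table | All-AE table | Non-TEAE listing |
|---|---|---|---|---|
| First PDT of a cycle to last PDT + 28 days | any | yes | yes | no |
| Later, up to Visit 5 or 8 | at least possibly related | yes | yes | no, under the TEAE definition |
| Later, up to Visit 5 or 8 | unrelated or unlikely related | **no** | yes, seriousness not shown | yes |

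The rule works on onset. A death after the window from an event that began inside it is still a fatal TEAE.

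**Threshold for the fatal-TEAE table.** More than 5 events means 6 or more. Counting one fatal event per death among 186 subjects, the binomial probability P(X ≥ 6) is as follows. The death rates are assumptions; the documents give none.

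| Assumed death rate | P(X ≥ 6) |
|---|---|
| 0.5% | 0.04% |
| 1% | 1.2% |
| 2% | 17.1% |
| 3% | 48.6% |

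At the low rates the dedicated table would very probably not be produced.

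**The case against.** The case for leaving the plan alone has several sound parts.

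- **The events are not lost.** A reader might infer that late serious events appear only in a listing, or that the report could not state SAE and death counts by arm. The documents do not support either reading. Every AE of the observation period in treated subjects enters the all-AE table per arm, and non-TEAEs are listed. Protocol 8.3.1 requires seriousness criteria to be recorded, so a count by hand should be possible. What is missing is a described table that makes the count.
- **Fatal TEAEs are not hidden by the threshold.** Death is an SAE criterion (Protocol 8.1.2), so each fatal TEAE enters the serious-TEAE table, which has no minimum. The threshold governs only the additional table.
- **The SAP did not narrow the protocol on deaths.** Protocol 11.3.4 itself focuses the analysis on TEAEs and restricts the death and discontinuation tables to them, subject to a reasonable number of events. The SAP puts a figure on that condition.
- **Neighbouring items are covered.** Protocol 11.3.1 and SAP 4.1 tabulate reasons for discontinuation without a TEAE or count condition, so the point does not extend to withdrawals. New AK, NMSC and melanoma since screening have their own table in SAP 4.5, not limited to the TEAE window.
- **Appendix A was not available.** It may already hold an all-SAE table.

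All of this stands, and it limits the size of the point. It does not supply the missing summary: a named safety variable has no described table for the full period, and for late events the serious count still depends on causality.

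**Conclusion.** The point holds in a limited form. As described in SAP 4.5, the by-arm serious-event table leaves out SAEs, fatal ones included, that begin more than 28 days after the last PDT of a cycle and are judged unrelated or unlikely related. That period is about half of each 12 weeks. It would be tempting to say more than half, but at a two-week PDT interval it is exactly half on the nominal schedule, and less if the 12-week visit is early.

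If such SAEs occurred at a constant rate over the cycle, about half of them would be missing from the table. This is an assumption; the documents give no SAE rate, so the number of events affected is unknown. The conclusion also assumes that Appendix A holds no all-SAE table. No efficacy test, alpha, power or data collection is affected. This is a gap in safety reporting that is cheap to close.

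**What to change.** In SAP 4.5, add a by-arm table, with subjects and events, of all SAEs and all deaths with onset from PDT-1 to the end of the clinical observation period (Visit 5 or Visit 8). Produce it whatever the TEAE window, the causality assessment or the number of events, so that a count of zero is also shown. Keep serious TEAEs as a subset. If Appendix A already includes such a table, align the text of SAP 4.5 with it.

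The cost is a few lines of SAP text and one or two extra tables from data already collected.

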#### Local reactions in the treatment field(s)

Local reactions, i.e. local skin reactions and local discomfort as assessed by investigator, are documented on AE page and can be identified as AEs with CRF question 'Is this (S)AE within a treatment field?' answered with 'yes' and are related (defined as possibly, probably, or definitely related, or with missing relationship) to IMP or medical device. Variable will be 'yes' if local reaction is documented at least once. Otherwise, variable will be 'no'. TEAEs identified as local reaction will be tabulated separately by intensity (mild/moderate/severe/unknown) separately for each PDT cycle. Therefore, local reactions with time of onset on or after the time of PDT-1 and before the time of PDT-3 will be categorized to PDT cycle 1. Local reactions with time of onset on or after the time of PDT-3 will be categorized to PDT cycle 2. If PDT-1 and/or PDT-3 are not available, the dates of PDT-2 and/or PDT-4 will be used for calculation respectively. If unclear due to incomplete start time/date of local reactions or PDT, local reactions will be categorized to PDT cycle unknown. Furthermore, the worst intensity (none/mild/moderate/severe) of at least one occurred PTs will be presented for local reactions. Thereby not available local reaction will be presented as intensity none. Missing or unknown intensity will not be considered for worst intensity analysis. Additionally, the frequency of any TEAEs identified as local reaction will be presented together with the respective CIs for each treatment group.

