Subjects will be randomized to a verum and a vehicle group at a ratio of 4:1, respectively. During randomization, a stratification into subjects with 1 or ≥ 2 lesion(s) and center will be considered to avoid imbalance in subjects with >1 lesions across treatment arms. The vehicle does not contain the active ingredient 5-ALA but is indistinguishable from BF-200 ALA with respect to color, appearance, and texture. The planned sample size will ensure at least 90% power on a significance level of 0.1% ($\alpha=0.001$). BF-200 ALA or vehicle will be administered by study personnel who have been intensively trained in performing PDT with the study medication. No other illumination devices besides BF-RhodoLED® may be utilized throughout the study.

Since visible application site effects are expected to occur in the BF-200 ALA group, an investigator will be responsible for all clinical assessments before and after treatments, but PDTs and all assessments within the 1st week following PDT will be applied by a second investigator or delegated person. Both investigators (or delegated person) are not entitled to exchange information in order to maintain the blinded status.

Risk-benefit analysis

All subjects participating in this study will receive surgical excision of the Main Target Lesion after the 1st or 2nd treatment cycle (12 weeks after PDT-1 or PDT-3) which represents the current standard in the treatment of sBCC. If additional lesions are included in the study (Additional Target Lesions) and these lesions are assessed as clinically cleared 12 weeks after the last PDT cycle, the lesions will not be excised in order to minimize the burden of the subject. However, they will be observed during

follow-up. The Additional Target Lesions will not be included in the calculation of the primary endpoint since no histological data are available. They will, however, contribute to the hierarchical testing of key secondary endpoints, further secondary endpoints and safety. Additional Target Lesions that remain clinically apparent 12 weeks after the 2nd PDT cycle will be treated at the discretion of the investigator. Irrespective of the treatment outcome all subjects will be regularly monitored during the follow-up period.

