7.3.2 Safety data

Adverse events

At each visit and during the phone contact(s), subjects will be asked indirectly regarding (S)AEs. Subjects will also be questioned indirectly to determine whether they had any pain, burning, itching, urticaria-like symptoms, or any other adverse events. For further information see [Section 8](#).

Local skin reactions, local discomfort, and pain

Local skin reactions in the treatment field(s) (also referred to as application site skin reactions) will be evaluated separately by the investigator (or equally qualified person) at each clinical visit during and after PDT. The observations will be documented in the source data and in the eCRF, including date and the time frame of the treatment (starting and ending point, as well as duration of the treatment).

The below mentioned AE intensity grading should be used.

The **local skin reaction** categories listed below will be checked by visual inspection of the treatment field(s) by a designated member of the study team during the visits (and documented in source and in the eCRF).

- Erythema
- Edema
- Induration
- Vesicles
- Erosion
- Ulceration
- Scaling/flaking
- Scabbing/crusting
- Weeping/exudate
- Others

For the investigator (or delegated person's) assessment the following 4-point scale should be used to assess the severity of local skin reaction in the treatment areas:

- 0 = no reaction
- 1 = mild reaction
- 2 = moderate reaction
- 3 = severe reaction.

In addition to the investigator (or delegated person's) assessments of local skin reactions, subject-reported local discomfort and pain during PDT for each subject will be recorded as reported by the subject (on subject questionnaire) and as assessed by the investigator (or delegated person) (as AE) and documented.

The **local discomfort** (also referred to as application site discomforts) categories listed below will be recorded according to the subject's complaint by a designated member of the study team during the PDT visits:

- Burning
- Itching
- Others

Subjects will be asked to assess local discomfort events as none, mild, moderate, severe (4-point scale see above) on the subject questionnaire. The severity result indicated by the subject should be confirmed/ assessed by an investigator or delegated person for documentation of the local discomfort.

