Pain reported during/following PDT will be assessed using an 11-point numeric rating pain scale (NRPS) assessment by the subject (see [Appendix C](#)). The assessed pain should be additionally documented in the eCRF. Further, the NRPS result indicated by the subject should be transformed for documentation in the AE eCRF page as follows: pain 1-3 = mild, 4-7 = moderate, 8-10 = severe.

If possible, each subject should be assessed by the same investigator(s)/staff personnel at each visit.

At each visit or during the phone contact(s) after the PDT sessions, subjects will also be asked if they have experienced any adverse reaction since their previous clinic visit using questions like "Have you noticed anything in the study surrounding areas since we last saw you?" Any signs or symptoms reported by the subject that correspond to one of the 10 local skin reaction categories and/or 3 local discomfort categories listed above should be scored for severity according to the subject's response to the following question: "How much, if any, difficulty or disruption has this (sign) caused you?"

Using the information provided by the subject, the clinical staff should record the most severe reaction reported by the subject in each category with start and stop date (if applicable) using the descriptors listed below:

- 0 = none (no reaction recalled by the subject)
- 1 = mild (the subject is aware of the signs and symptoms, but the signs and symptoms are well tolerated and do not interfere with daily activities)
- 2 = moderate (the signs and symptoms are sufficient to restrict, but not to prevent, usual daily activities for the subject)
- 3 = severe (the subject is unable to perform usual daily activities).

New lesions

Assessment of new lesions during the clinical observation period and the FU part of the study will include new NMSC and melanoma, as well as new AK lesions.

New lesions with indication of localization(s) and reference to the treatment field(s) should be reported as (S)AE. These new lesions may be treated during the clinical observation period with

physical measures at the discretion of the investigator and without restriction during the follow-up period. Please refer to [Section 6.2 Concomitant treatments for restrictions](#).

Physical examination

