#### 5 Changes from Protocol

- The protocol (version 3.0 of 17Jul2018) states: 'The frequency of local skin reactions at the treatment field and of local discomfort will be presented together with the respective CIs for each treatment group.'. Local skin reactions are not separately evaluated using a 4-point scale by visit and illumination field. Local skin reactions are documented as AEs and are included in analysis of AEs defined as local reactions. No separate frequency tables with the respective CIs of local skin reactions will be created.
- The protocol (version 3.0 of 17Jul2018) states: 'TEAEs are defined as all AEs with onset or worsening after treatment with randomized IMP within 4 weeks after each PDT cycle (until Visit 4 or Visit 7, respectively).'. This definition is adapted in SAP to consider the start time of AEs and treatment and to avoid:
  - confusion between worsening of the illness, which is to be documented as AE, and worsening of AEs (change of intensity).
  - wrong assignment to TEAE, due to allowed per protocol time window for Visit 4 and Visit 7, respectively.

The adapted TEAE definition is: 'TEAEs are defined as all AEs with time of onset on or after the time of treatment with IMP within 4 weeks (28 days) after each PDT cycle. If time of onset of AEs is not within 4 weeks (28 days) after each PDT cycle but is identified to be at least possibly related to IMP or medical device, AEs will be assumed as TEAEs.'.

- Small wording adaptions were performed within this SAP to be consistent in the analyses, e.g. 'patient' vs. 'subject', etc.
- □ The protocol (version 3.0 of 17Jul2018) states: "... subjects' overall satisfaction with the treatment will be assessed ...using a 4-point scale...". Subjects' satisfaction with treatment was not evaluated on a 4-point scale, they were asked if they would choose the PDT treatment again in the future.

[figure not shown]

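### SAP 4.5 replaces the protocol's local skin reaction table with a pooled, relatedness-filtered adverse event variable, and SAP section 5 does not declare the filter

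*SAP*

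**What the plan says.** Protocol 11.1.6 names as a safety variable "Local skin reactions at the treatment field(s) assessed by the investigators". Section 7.3.2 gives the method: ten categories (nine named signs plus Others) that "will be checked by visual inspection of the treatment field(s) by a designated member of the study team during the visits", each scored 0 to 3. Section 11.3.4 promises a frequency with confidence interval per arm, for skin reactions and for discomfort. None of these sections asks what caused the sign. Section 7.3.2 also sends pain to the adverse event page, converting the numeric rating as "pain 1-3 = mild, 4-7 = moderate, 8-10 = severe".

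SAP 2.4 still lists the skin reaction variable. In SAP 4.5, under the heading on local reactions, the data source is stated as "Local reactions, i.e. local skin reactions and local discomfort as assessed by investigator, are documented on AE page". An event counts if it lies within a treatment field and if it and its like "are related (defined as possibly, probably, or definitely related, or with missing relationship) to IMP or medical device". A subject with no such event is set to no, or to intensity none. The outputs are intensity by PDT cycle, worst intensity, and this: "Additionally, the frequency of any TEAEs identified as local reaction will be presented together with the respective CIs for each treatment group".

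SAP section 5 says the 4-point grading by visit and field is not done and the separate table with confidence intervals is dropped. It adds: "Local skin reactions are documented as AEs and are included in analysis of AEs defined as local reactions". It does not say that this definition carries a causality condition or merges skin signs with discomfort.

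**The concern.** The two documents answer different questions. The protocol asks how many subjects in each arm showed a visible skin reaction in the treated field. The SAP asks how many had any in-field complaint or sign that someone attributed to the drug or the lamp. For a topical treatment whose main expected harm is local, the first question is the one a reader of the safety section wants answered against vehicle.

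Three things follow. The skin-sign frequency can no longer be read from a field-restricted table. The severity of the pooled variable may reflect pain rather than skin. And a causality judgement enters a variable that did not have one, in a trial where the protocol separates the two assessors for this reason: "Since visible application site effects are expected to occur in the BF-200 ALA group". If staff can guess the arm, their causality rating could depend on it.

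**Working it through.** The plan gives no figure for local reactions, so there is nothing to reproduce. The check is a comparison of texts, followed by two illustrations on assumed rates.

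**1. Definitions side by side**

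| | Protocol 7.3.2, 11.1.6, 11.3.4 | SAP 4.5 and 5 |
|---|---|---|
| Content | Ten skin-sign categories | Skin signs and discomfort together; pain if recorded as an in-field related event |
| Source | Visual inspection, scored 0–3 | Adverse event page |
| Causality | None required | Possibly, probably or definitely related, or missing |
| Output with interval | Skin reactions; discomfort | Any pooled local reaction; discomfort from the questionnaire |

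The SAP's local-reaction text does not name pain. Its inclusion follows from protocol 7.3.2, which records pain as an adverse event.

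**2. What the filter drops.** Protocol 8.3.1 has five causality levels. The SAP keeps the top three and missing values, and drops unrelated and unlikely related. The protocol's wording for unlikely related still leaves a causal role open. Relatedness enters once more in the SAP's definition of treatment-emergent events: onset more than 28 days after a cycle's last PDT counts only if the event is at least possibly related.

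**3. What remains elsewhere.** SAP 4.5 tabulates all adverse events and treatment-emergent events by system organ class and preferred term, and the treatment-emergent ones also by intensity and by relationship. It lists every treatment-emergent event. These outputs have no relatedness filter, but they are not restricted to the treatment field.

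**4. Pooling (assumed rates).** Let s be the share of subjects with a skin sign and q the share with discomfort or pain. Under independence, P(any) = 1 − (1 − s)(1 − q).
- s = 0.30, q = 0.50: 1 − 0.70 × 0.50 = 65%.
- s = 0.30, q = 0.80: 1 − 0.70 × 0.20 = 86%.

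Without independence the bounds are max(s, q) to min(1, s + q): 50–80% and 80–100%. A skin-sign rate of 30% cannot be recovered from any of these.

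**5. Filter (assumed rates).** Counted rate = true in-field rate × share of subjects with at least one event judged related. Take 95% of active and 50% of vehicle subjects with a reaction, a true difference of 45 points, with all active-arm reactions judged related.
- Vehicle share 100%: 95 − 50 = 45 points.
- Vehicle share 80%: 95 − 40 = 55 points.
- Vehicle share 50%: 95 − 25 = 70 points.

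The whole distortion comes from the assumed vehicle share. Some widening could arise without biased raters, because one related event is enough to count a subject. If each event is judged related with probability 0.70, independently and equally in both arms, a subject with four events is counted with probability 1 − 0.30⁴ = 99%, and a subject with one event with probability 70%.

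**6. Severity.** A pain score of 8 to 10 becomes a severe event. If it is in-field and related, a subject with mild erythema and that pain score has a pooled worst intensity of severe.

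**The case against.** A reader might infer that the protocol's endpoint has been replaced by a causality opinion biased by arm, so that the drug's excess will be overstated. The documents do not support that.

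- Filtered events do not vanish. They appear in the general tables described above, including the table by relationship. Only the field-restricted summary loses them.
- Protocol 8.3.1 makes most early reactions at least possibly related. That level covers an event linked in time to drug or lamp even when another cause is recognised. Unlikely related needs an atypical time course and no known response pattern. A sign that follows gel, dressing and light fits the former, in vehicle subjects too; the protocol's risk-benefit text says PDT effects cannot be ruled out for them. Missing relationships count as related.
- The person who applies PDT makes the safety evaluations at PDT visits and phone calls, not at every visit, and section 8.3.1 leaves causality to the investigator's judgement. The protocol's own visual grading is also done by staff who see the reactions.
- Neither document gives a vehicle reaction rate or a share judged related. For earlier trials, protocol 8.1.3 says only that nearly all subjects reacted.
- Discomfort and pain have their own analyses. The worst-intensity sentence refers to preferred terms and may be meant term by term, in which case pain would not set the grade for erythema.

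All of this stands as a limit on size and direction. It does not restore the missing output. Any preferred-term breakdown of the local-reaction tables would still be related-only, and no row gives any in-field skin sign with an interval.

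The objection also warns against a simple repair. Counting every in-field event would bring in wound events after the Visit 5 excision in partial responders, which fall within the second cycle's window, and new lesions, which are recorded as adverse events. Excision at Visit 5 depends on response, so this contamination could itself differ by arm.

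**Conclusion.** The point holds as a gap between protocol and SAP. The promised per-arm frequency with interval for local skin reactions is replaced by a pooled, related-only variable; the pooled worst intensity can be set by pain; and SAP section 5 discloses the lost table but not the relatedness filter. This rests on the text alone, except that the role of pain relies on protocol 7.3.2 and on reading worst intensity across terms.

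The numerical effect cannot be derived from the documents; the illustrations show only how the definitions behave under assumed rates. Causality rating that differs by arm is a possible risk, not something the documents show. These safety analyses are descriptive, so neither the primary test nor its error rate is affected. The change is worth making because it is cheap and gives back what the protocol promised.

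**What to change.** In SAP 4.5, add a table per arm, with confidence interval and worst intensity, of in-field treatment-emergent events whose terms match the skin-sign categories of protocol 7.3.2, regardless of relatedness and separate from discomfort and pain. Exclude new lesions. Show events at the Main Target Lesion site with onset after its excision separately. State how events beyond the 28-day window are treated, since the SAP admits those only if related. Keep the related-only pooled table as supportive. List both the relatedness filter and the pooling in SAP section 5.

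The cost is a few extra tables and some mapping of event terms to the protocol categories, using the field flag, term and intensity already on the adverse event page. The vehicle frequency becomes somewhat less specific to the drug, which is why the related-only table should stay beside it.
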